# 5 Overall Study Design

This is a 6-month prospective, randomized, double-blinded, placebo-controlled clinical trial investigating the efficacy, safety, and tolerability of two different doses of buntanetap or placebo in patients with early PD.

CL.

Qualified subjects will be randomly assigned at a 1:1:1 ratio to one of three treatment arms: buntanetap 10 mg, buntanetap 20 mg, and placebo after a screening period of up to 42 days.

MDS-UPDRS, CGIS, WAIS IV, and MMSE will be assessed in clinical OFF-state during visits, i.e., after subjects having stopped medications of SOC Parkinson's disease 12 hours before clinical visits.

PGIC will be assessed in clinical ON-state during visits, i.e., subjects are allowed to take their SOC Parkinson medication during buntanetap treatment.

450 subjects with early PD will be randomized to 10 mg, 20 mg of buntanetap QD or placebo.

They will undergo a Screening Visit, and if they provide Informed Consent (IC) and are considered eligible per the inclusion and exclusion criteria, will proceed to participate in the treatment period. Randomized subjects will visit the clinic for the first-time dosing in clinic with administration of 10 mg or 20 mg of buntanetap or placebo, followed by an at home dosing period of 6 months, with daily administration of 10 mg or 20 mg of buntanetap or placebo.

Subjects will be required to visit clinics at 1 month, 2 months, 3 months, and 6 months (end-of-trial), where they will undergo study procedures that include safety assessments (AE and concomitant medication monitoring, 12-lead ECGs, clinical laboratory testing, vital signs assessments, and physical/neurological examinations), psychometric tests (MDS-UPDRS, WAIS, MMSE), PGIC (ON-state), and CGIS.

The Schedule of Events is shown in Appendix 1.

#### 6 Determination of Sample Size

A sample size of up to 450 subjects (1:1:1 randomized to 10 mg, 20 mg buntanetap and placebo respectively) was determined.

Qualified subjects will be randomized at a 1:1:1 to one of the following three treatment groups: buntanetap 10 mg, 20 mg QD and placebo. A sample size of 360 (120 per treatment group) will have 90% power to detect a treatment difference at a two-sided 0.025 significance level. In the sample size calculation, it was assumed a treatment difference of 2.55 and a common standard deviation (SD) of 5.59 based on historical data of MDS-UPDRS Part II+III. Approximately 450 subjects will be randomized (approximately 150 per arm) to account for 120 subjects calculated from the power analysis plus screen failures and dropout rates.

#### 7 Data Sets to be Analyzed

Subjects in this study must be in accordance with the criteria specified below. Subjects who do not meet all inclusion criteria, disease diagnostic criteria, or who meet any exclusion criteria may not be randomized into the study without prior approval from the Project Directors and Medical Monitor. Membership in the analysis sets will be determined in a Pre-Analysis review meeting (see Section 8.2) before unblinding.

The following analysis sets will be used for the statistical analysis and presentation of data:

- The Enrolled set (ES) will include all subjects who signed IC and meet all inclusion and exclusion criteria. All data collected from ES will be presented in listings and if relevant in tables and/or graphs. Screening failures will have selected data be presented in a separate listing if needed.
- The Intent-to-Treat set (ITT) will consist of all subjects who are randomized. The primary efficacy analyses will be based on the ITT.
- The Modified Intent-to-Treat set (mITT) will consist of all subjects who randomized, take at least 1 dose of the study drug, and have at least 1 post-baseline assessment. The mITT will be used to support the primary efficacy analyses.
- The Safety analysis set (SAF) will be the primary safety analysis set and will consist of all
  randomized subjects who receive at least 1 dose of the study drug. The safety analyses will
  be based on the SAF.
- The Per-protocol set (PPS) will consist of all mITT subjects who complete at least 145 days treatment exposure (Last dose date First dose date + 1 >= 145 days) without any major protocol deviations that potentially could impact the primary efficacy endpoint. The PPS will be used to support the primary and secondary endpoints as supportive analyses.
- The PK set will analyze all available data from safety subjects receiving buntanetap and with at least one sampling profile allowing derivation of at least one PK parameter. Intense PK

subgroup is only in the US. 16-people per group will go through 10hr sampling timepoints at 0, 1hr, 1.5hr, 2hr, 3hr, 4hr,5hr, 6hr, 7hr, 8hr, 9hr, and 10hr (±10 mins for all collection timepoints).

Protocol deviations leading to exclusions from PPS include but are not limited to the following:

- Non-fulfilment of all inclusion criteria
- Fulfilment of at least one exclusion criterion
- Use of certain concomitant medications (for details see section 8.3.11)

The final criteria for the PPS, regarding which protocol deviations that warrant exclusion, will be determined during the pre-analysis review when all data on protocol violations/deviations are available and before breaking the blind.

Baseline presentations will be based on the SAF.

Safety presentations will be based on the SAF.

Exposure to study drug will be given for the SAF.

The ITT and mITT will be analyzed according to randomized (planned) treatment. Safety and PPS will be analyzed on actual treatment.

Plasma concentration-time data for buntanetap will be based on the SAF. PK parameters derivations and statistical analyses in a separate PK SAP will be based on the PK set.

#### 8 Statistical and Analytical Plans

#### 8.1 Changes to the Planned Analyses

There have been no changes in the planned analyses in the study protocol.

#### 8.2 **Pre-Analysis Review**

A pre-analysis review meeting will be held prior to database lock. During this meeting, the assignment of subjects to the analysis sets will be discussed and decided reviewing

- Screen failures with reason for failure
- Discontinued subjects with reason for discontinuation
- Protocol deviations
- Available efficacy data by visit
- Preliminary subjects' classifications of analysis sets as far as possible

#### 8.3 Hypothesis and Statistical Methods

For tests of statistical significance on efficacy variables the significance level (p-value) will be provided together with the 95 percent confidence intervals (CI) of the mean, minimum, median, first and third quartiles and maximum.

#### 8.3.1 Level of Significance, Multiple Comparisons and Multiplicity

There are two active treatment groups (10 mg and 20 mg) in the study. Each of the two active treatments will be compared to the control (two hypothesis tests for the primary endpoint). The comparison of each of the two treatment groups against control for the primary endpoint will be performed using the Hochberg step up procedure, where if the largest p-value is <0.05, then the null hypothesis will be rejected for both groups. If the largest p-value is >0.05, then the critical value for the second test will be at two-sided 0.025.

To control for study-wise type 1 error rate, a fixed-sequence hierarchical testing procedure will be applied to adjust for multiplicity arising from multiple secondary endpoints. The hierarchical testing order for the secondary endpoints are:

- 1. Change from baseline to Month 6 in the sum of MDS-UPDRS Part II+III (OFF-state)
- 2. Change from baseline to Month 6 in MDS-UPDRS Part III (OFF-state)
- 3. Change from baseline to Month 6 in MDS-UPDRS Total score (OFF-state)
- 4. Percentage of Responders with "Much Improved" or "Very Much Improved" on PGIC (ON-state)
- 5. Change from baseline to Month 6 on CGIS (OFF-state)

If the primary endpoint of both dose groups are statistically significant, the secondary endpoints for each dose group will be tested in a hierarchical manner at alpha 0.025. If the primary endpoint of a specific dose group is statistically significant, the secondary endpoints for that dose group will be tested in a hierarchical manner at alpha 0.025. If the primary endpoint of both dose groups are not statistically significant, the hypothesis testing for all subsequent endpoints will be considered exploratory. Two flowcharts are also presented in the following.

All other exploratory endpoints are considered supportive and no adjustment for multiplicity will be applied.

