## 1 Abbreviations

αSYN	Alpha-synuclein
Αβ	Amyloid beta
AD	Alzheimer's disease
ADL	Activities of daily living
AE	Adverse Event
APP	Amyloid β Precursor Protein
AR(1)	First-order Autoregressive
ATC	Anatomical Therapeutic Chemical
AUC	Area under the curve
C max	Maximum plasma and CSF concentration
CGIS	Clinical Global Impression of Severity
CI	Confidence interval
CL	Clearance
СМ	Concomitant medication
СР	Conditional Power
CSF	Cerebrospinal Fluid
CSP	Clinical Study Protocol
C-SSRS	Columbia Suicide Severity Rating Scale
CV	Coefficients of variation
DSMB	Data Safety Monitoring Board
ECG	Electrocardiogram
eCRF	Electronic Case Report Form
ES	Enrolled set
FDA	Food and Drug Administration
GFAP	Glial Fibrillary Acidic Protein
IC	Informed Consent
IDMB	Independent DSMB
IMP	Investigational Medicinal Product
ITT	Intent-to-Treat set
LSM	Least Square Mean
MAR	Missing at Random
MCMC	Markov Chain Monte Carlo
MDS-UPDRS	Movement Disorder Society-United Parkinson's Disease Rating Scale
MedDRA	Medical Dictionary for Regulatory Activities
mITT	Modified Intent-to-Treat set
MMRM	Mixed Model for Repeated Measures
MMSE	Mini-Mental State Examination

MNAR	Missing Not at Random
NFL	Neurofilament Light
PD	Parkinson's disease
PGIC	Participant Global Impression of Change
PK	Pharmacokinetic
PPS	Per-protocol set
PT	Preferred Term
QD	Once a Day
RCTC	Rheumatology Common Toxicity Criteria
SAE	Serious Adverse Event
SAF	Safety analysis set
SAP	Statistical Analysis Plan
SD	Standard Deviation
SOC	System Organ Class / Standard of care
Τ1/2	Half-life
tau	Tau protein
TDP-43	TAR DNA-binding Protein 43
TEAE	Treatment-Emergent Adverse Event
t max	Time to peak drug concentration
TOEPH	Heterogeneous Toeplitz
UN	Unstructured
WAIS-IV	Wechsler Adult Intelligence Scales, 4th edition
WHO	World Health Organization

Version Number	Version date	Section(s) Updated	Change since previous version (with reason)
Draft 0.1	24-OCT-2022	All	First version
Draft 0.2	03-NOV-2022	All	Internal review comments incorporated
Draft 0.3	17-NOV-2022	All	Sponsor first review comments incorporated
Final 1.1	09-DEC-2022	All	Final version
Final 1.1 Amendment	25-APR-2023	All	Bonferroni method was updated to Hochberg method. Revised the randomized sample size and evaluable sample size as needed in the Interim Analysis section for consistency with the protocol.
Final 2.0 Amendment	07-DEC-2023	All	FDA comments incorporated

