#### Change from baseline to Month 6 in the sum of MDS-UPDRS Parts II+III – OFF-state

The MDS-UPDRS is a 50-item rating scale designed to assess Parkinson's disease-related disability and impairment. The scale comprises four parts: Part I evaluates mentation, behavior, and mood symptoms; Part II evaluates ADL; Part III evaluates motor function; and Part IV evaluates complications of dopaminergic therapy. Part II contains 13 questions which are to be completed by the participant (range 0-52). Part III contains 33 scores based on 18 items (Range 0-132). MDS-UPDRS Part II and III combined score equals the sum of Parts II and III (Range 0-184). A higher score indicates more severe symptoms of PD.

MDS-UPDRS Parts II+III will be analyzed by MMRM, similar to the primary efficacy endpoint.

Change from baseline to Month 6 in the MDS-UPDRS Part III – OFF-state

Part III contains 33 scores based on 18 items (Range 0-132).

MDS-UPDRS Part III will be analyzed by MMRM, similar to the primary efficacy endpoint.

Change from baseline to Month 6 in the MDS-UPDRS Total score - OFF-state

The UPDRS is a 50-item rating scale designed to assess Parkinson's disease-related disability and impairment. The scale comprises four parts:

Part I evaluates mentation, behavior, and mood symptoms;

Part II evaluates ADL;

Part III evaluates motor function; and

Part IV evaluates complications of dopaminergic therapy.

The MDS-UPDRS Total score is the sum of the subscale scores for Parts I to III and ranges from 0 to 236, with higher scores reflecting greater severity. MDS-UPDRS will be assessed by the investigator at baseline and each visit at the clinic (Month 1, Month 2, Month 3, and Month 6).

MDS-UPDRS Total score will be analyzed by MMRM, similar to the primary efficacy endpoint.

Percentage of responders with "Much improved" or "Very much improved" on PGIC - ON-state

The PGIC is the participant-reported outcome. The qualitative assessment of meaningful change will be determined by the participant in response to the question, "Compared to your condition at the beginning of treatment, how much has your condition changed?" Scores are

1= very much improved

2= much improved

3= minimally improved

4= no change

5= minimally worse

6= much worse

7= very much worse

The assessment is done during visits at the clinic (Month 1, Month 2, Month 3, and Month 6) and ONstate i.e., subjects were allowed to treat the PD with SOC medication.

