According to Chen, Yuan and Li (2018), the bias and error rate using the original maximum likelihood estimator (MLE) point estimator and confidence interval should be small and appropriate to use in the final analysis. In addition, the interim analysis was done using the original primary endpoint MDS-UPDRS Part II+III. Based on the Agency's feedback, the original primary endpoint is changed to MDS-Page 24 of 28 UPDRS Part II, and MDS-UPDRS Part II+III is kept as a secondary endpoint. Thus, the results of interim analysis are not relevant to the new primary endpoint. With a sample size of 174 per arm, the study will have 90% power to detect a treatment difference of 3 assuming a common SD of 8, based on a 2-sided t-test with alpha of 0.025.

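### SAP 8.3.1 tests a lone winning dose's secondaries at a further 0.025 after full Hochberg, so study-wise control fails if the other dose is null on Part II and the winner has a null secondary that is reached often enough

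*SAP*

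**What the plan says.** SAP 8.3.1 compares each dose with placebo on Part II by Hochberg: "if the largest p-value is <0.05, then the null hypothesis will be rejected for both groups"; otherwise the smaller p-value is tested at two-sided 0.025. For the five secondaries it states: "To control for study-wise type 1 error rate, a fixed-sequence hierarchical testing procedure will be applied". The order is Part II+III, Part III, Total score, PGIC responders, CGIS.

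Three branches follow. If both primaries are significant, each dose's secondaries are tested in order at 0.025. If one dose's primary is significant, "the secondary endpoints for that dose group will be tested in a hierarchical manner at alpha 0.025". If neither is, everything after the primary is exploratory.

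The prose does not truncate Hochberg, pass alpha on by rule, or require both doses to win before a lone winner's secondaries are opened. Protocol 6.9 says only that Hochberg controls the familywise error and refers to the SAP. Section 8.3.1 also mentions two flowcharts, which are not visible in the extracted text. The SAP's version history records that the "Bonferroni method was updated to Hochberg method".

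**The concern.** Hochberg can spend the whole 0.05 on the two primary tests. Once one dose clearly works, its p-value is small, the larger p-value belongs to the other dose, and that dose is in effect tested at 0.05. If that dose is truly null, all of the alpha is exposed there. The lone-winner branch then adds 0.025 for the winner's secondaries, although nothing is left to fund it. A chain of 0.025 per dose fits a Bonferroni split, in which each dose owns its 0.025 from the primary onward. It does not fit full Hochberg.

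At stake is the status of the secondary claims. If one dose wins and the other does not, the SAP would present the winner's secondaries as confirmatory under study-wise control that does not hold in this configuration.

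**Working it through.** **Inputs from the documents.** 174 per arm, 1:1:1 with a shared placebo (SAP 8.10.2 and 6), so the two dose contrasts correlate at 0.5. For Part II, SAP 8.10.2 states "90% power to detect a treatment difference of 3 assuming a common SD of 8, based on a 2-sided t-test with alpha of 0.025". The testing rules are those of SAP 8.3.1. II+III is built as the SAP defines it: "MDS-UPDRS Part II and III combined score equals the sum of Parts II and III".

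**Inputs assumed.** Part III SD 6–12 and II–III correlation 0.2–0.6. The documents give neither.

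**1. The plan's own figure.** Noncentrality = 3 / (8 × √(2/174)) = 3.50. With critical value 2.24 for two-sided 0.025, power is 0.896 (0.893 by noncentral t). The stated 90% is reproduced.

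**2. Configuration.** Dose A has the planned Part II effect, dose B is null on Part II, and dose A is null on Part III. An error is a false Part II claim for B or a false Part III claim for A.

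Error = P(B's primary rejected) + P(A wins alone and Part III is falsely claimed)

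**3. First term.** From the bivariate normal with correlation 0.5: 0.0464. It rises towards 0.05 as A's effect grows.

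**4. Second term.** By simulation of the written rule (6 million draws per cell; Part III SD 6 or 12, correlation 0.2 or 0.6): about 0.011 to 0.0116. It is nearer 0.0125 than 0.025 because II+III must be significant first. At the planned effect that mostly lets through Part III errors in the favourable direction, which is half of 0.025. Overlap with B's false primary removes a little more.

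**5. Total at the planned effect.** 0.0575–0.0580, about 5.7–5.8%. With 164 evaluable per arm (174 × 0.94, the roughly 6% dropout in SAP 8.10.2) it is 5.7%. Counting only favourable-direction errors leaves it at 5.7–5.8%. Outside the assumed range, a Part III SD of 4 with zero correlation gives 6.2%.

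**6. Larger effect.** With a Part II effect of 6, twice the plan: 0.0614–0.0726, about 6.1–7.3%.

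**7. Upper limit.** The additive bound is 0.05 + 0.025 = 0.075. If the null secondary is always reached and independent of B's test, 1 − 0.95 × 0.975 = 0.0738.

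**8. How often the null secondary must be reached.** At the planned effect, for a null secondary reached independently of the other tests:

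| Reached | Familywise error |
|---|---|
| 10% of the time | 4.75–4.86% |
| 30% of the time | 4.95–5.3% |
| always | 5.7–6.8% |

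**9. Where the scheme holds.**
- Global null: any primary rejection has probability 0.0480, and a secondary is tested only after such a rejection.
- Both doses work on Part II: two chains at 0.025 total at most 0.05.
- One dose works and all its secondaries are real: 0.0464.
- Each dose's chain taken alone is held at 0.025.

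**The case against.** The strongest reply is that the failing case is one the sponsor does not expect. SAP section 3 says both 10 and 20 mg showed the best benefit in Phase 2a. If both doses work at the planned effect, exactly one wins in only 7.7% of trials, and there is then no excess. At the planned effect the excess is under one point. This limits the severity but does not rescue the claim: strong control must hold under every combination of true and false nulls, and 8.3.1 claims control without qualification. If only one dose works, exactly one wins in about 86% of trials, so the faulty branch is then the usual one.

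A reader might infer that the plan's own figures point to a null Part III, because SAP section 6 "assumed a treatment difference of 2.55 and a common standard deviation (SD) of 5.59 based on historical data of MDS-UPDRS Part II+III" and the later Part II difference is 3. The documents do not support that. The two figures come from different planning exercises and cannot be subtracted. For II+III to have SD 5.59 (variance 31.25) when Part II has SD 8, the II–III correlation would have to be (31.25 − 64 − 36)/96 = −0.72 at a Part III SD of 6, or (31.25 − 64 − 144)/192 = −0.92 at 12. Protocol 2.0 also reports Phase 2a improvement on Part III. A null Part III is a legitimate test case and nothing more.

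The flowcharts could restrict the lone-winner branch. That cannot be excluded, but the prose is explicit, and the two should agree.

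**Conclusion.** The concern holds. The study-wise control claimed in SAP 8.3.1 fails when three things are true together: one dose works on Part II, the other is truly null on Part II, and the winner has a truly null secondary that is reached often enough. With Part III as that secondary, the two-sided familywise error is about 5.7–5.8% at the planned effect, given the assumed SDs and correlations. The 6.1–7.3% range needs twice the planned effect, and 7.5% is a bound, not an estimate.

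Two broader readings are not supported. A null secondary in a winning dose does not break control by itself; the other dose must also be null on Part II. The primary analysis is not in question either: Hochberg controls the two Part II tests as intended. This should be fixed, but it affects only the status of a lone winner's secondary claims.

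**What to change.** Before unblinding, change the lone-winner rule in SAP 8.3.1 and make the two flowcharts match. Only SAP wording changes. Any one of these works; they are not ranked.

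- **(a) Require both doses.** Keep Hochberg. Open confirmatory secondaries, at 0.025 per dose, only if both doses are significant. Report a lone winner's secondaries with nominal p-values. Primary power is unchanged. The cost is no confirmatory secondary claim for a lone winner.
- **(b) 0.025 throughout.** Run each dose's primary and five secondaries at 0.025. This keeps the power stated in SAP 8.10.2 but gives up Hochberg's gain over Bonferroni. If one dose works, power falls from 89.9% to 89.6%. If both work, per-dose power falls from 93.1% to 89.6%, and power to win on both from 89.2% to 82.6%.
- **(c) Truncated Hochberg.** Both doses win if the larger p is ≤0.0375; otherwise the smaller p is tested at 0.025. A lone winner's chain runs at 0.0125 (0.0375 + 0.0125 = 0.05), and at 0.025 per dose if both win. Power lies in between: 89.7% if one dose works; 91.7% per dose and 86.7% on both if both work. The lone winner's secondaries have less power at 0.0125.

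At the planned effect, the highest simulated error under any of the three is 4.7%. With a Part II effect of 6 all three hold 5% within simulation error. If none is adopted, withdraw the study-wise control claim for a lone winner's secondaries.

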#### 8.3.2 Definitions

MMSE – OFF- state	Mini-Mental State Examination is a 30-point test, widely used test of cognitive function.
PGIC – ON-state	Participant Global Impression of Change is the participant-reported outcome.
	The qualitative assessment of meaningful change will be determined by the participant in response to the question, "Compared to your condition at the beginning of treatment, how much has your condition changed?" Scores are 1= very much improved; 2= much improved; 3= minimally improved; 4= no change; 5= minimally worse; 6= much worse; 7= very much worse
CGIS – OFF-state	Clinical Global Impression of Severity is a scale on the severity of movement impairment as assessed by the site rater. Site raters will be asked: Considering your total clinical experience with the Parkinson disease population, how ill is the patient's movement at this time? Answers were based on a 7-point scale, with 1= not assessed, 2= very mild, 3= mild, 4= moderate, 5= moderate severe, 6= severe, 7=extremely severe
WAIS-IV – OFF- state	In the digital symbol Wechsler Adult Intelligence Scales, 4th edition, coding test individuals are asked to record associations between different symbols and numbers within time limits. The Total score is the sum of all the correctly coded numbers.

MDS-UPDRS – OFF-state	Movement Disorder Society-Unified Parkinson's Disease Rating Scale is a 50-item rating scale designed to assess Parkinson's disease-related disability and impairment comprising the four parts:
	Part I - Non-Motor Aspects of Experiences of Daily Living
	Part II - Motor Aspects of Experiences of Daily Living
	Part III - Motor examination
	Part IV - Motor complications
Treatment- Emergent Adverse Event	Treatment emergent adverse events (TEAEs) are defined as undesirable events not present prior to medical treatment, or an already present event that worsens either in intensity or frequency following the treatment. If an AE starts at the same day as the study drug the start time of the AE will be compared with the start time of the administration of study drug. If the start time of the AE is at or after start time of administration of study drug the AE is a TEAE. If no clear assignment is possible due to incomplete or missing start dates, the AE will be counted as TEAE.
Baseline	Baseline will be the last assessment before or up to the first dosing of the study drug. This is valid for vital sign, laboratory data, and safety data, where a difference from baseline is derived. For diary data and questionnaire data, baseline will be the assessment at the baseline visit.
Height [cm]	All values collected in inches will be converted to cm as follows: Height [cm] = height [feet] * 30.48
Weight [kg]	All values collected in pounds will be converted to kg as follows: weight [kg] = weight [pounds] * 0.454
Relative day	The relative day of an event is derived as:
	Relative day = (Start date) - (Date of first administration of Investigational Medicinal Product (IMP) + 1
	For events occurring or starting before the date of first administration of IMP, the relative day is derived as:
	Relative day = (Start date) - (Date of first administration of IMP)
	In this way, there will be no Day 0. Day 1 is the same day as the day of first administration of IMP, and Day -1 is the day before.
Date format	All dates in analysis datasets and tables, listings and figures will be in

